#### 4.2.3 Exploratory Endpoints

- Dosimetric consequences on the PTV, lungs and kidneys as a result of patient setup variations
- Analysis of in vivo transit dosimetry using SNC PerFraction (Fraction N) for dose tracking and correlation with patient setup
- Comparison of linac based VMAT TBI vs. conventional TBI for treatment planning time
- Comparison of linac based VMAT TBI vs. conventional TBI for treatment delivery time
- Cost analysis of linac based VMAT TBI vs. conventional TBI
- Dosimetric consequences on the PTV, lungs, and kidneys as a result of patient setup variations.
- In vivo transit dosimetry using SNC PerFraction (Fraction N) for dose tracking and correlation with patient setup
- Linac based VMAT TBI planning time vs. department's previous cases for treatment planning time
- Linac based VMAT TBI treatment delivery time vs. department's previous cases for treatment delivery time
- Linac based VMAT TBI costs vs department's previous cases

## 5 Study Enrollment and Withdrawal

### 5.1 Inclusion Criteria

In order to be eligible to participate in this study, an individual must meet all of the following criteria:

1. Age  $\geq 10$  years
2. Patients undergoing related, unrelated (including cord blood) hematopoietic progenitor cell (HPC) transplant, in which the protocol requires  $\geq 12$  Gray of TBI, as part of the conditioning regimen.
  - a. For individuals  $\geq 18$  years old, conditioning regimens outlined per BMT SOP: CLNTX007: Selection of Conditioning Regimens for Blood and Marrow Transplantation – ADULTS.
  - b. For individuals  $< 18$  years old, conditioning regimens outlined per pediatric BMT SOP: CLNTX014: Selection of Conditioning Regimens for Blood and Marrow Transplantation – PEDIATRICS. Individuals  $< 18$  years old will be included are from New York, New Jersey and Connecticut.
3. Referral from the blood and marrow transplant (BMT) program for full-dose TBI, who meet inclusion and exclusion criteria per BMT SOPs.
  - a. BMT program will initiate referral, utilizing Form: 170102, Radiation Oncology Consultation.
  - b. Patients undergo pre-transplant testing, as defined in BMT SOPs: CLNAL002: Related (MRD, Haplo) Allogeneic Recipient Evaluation and Management or CLNAL011: Unrelated (MUD, MMUD, CBU) Allogeneic Recipient Evaluation and Management, per below.
    - i. BMT SOP's include baseline pulmonary function tests (PFTs). Patient with decreased FVC, FEV1 and or DLCO (adjusted for hemoglobin) or pulmonary history will have pulmonary consult, at the discretion of the BMT physician prior to undergoing myeloablative radiation.
    - ii. Medical history and physical by BMT provider.
    - iii. The following laboratory tests (additional testing may be required for positive results):
      1. ABO group and Rh type
      2. Red Blood Cell Antibody Screen.
      3. HLA typing and confirmatory typing
      4. HLA antibody screen, class I and II, performed within 30 days of transplant.
      5. Complete blood count (CBC) with differential.

#### CONFIDENTIAL

This material is the property of the NYU School of Medicine and Langone Medical Center. Do not disclose or use except as authorized in writing by the study sponsor

6. Basic metabolic panel, including glucose and to include at a minimum electrolyte evaluation of potassium, calcium, magnesium, and phosphorus.
7. Blood urea nitrogen (BUN)
8. Creatinine
9. Liver Function Tests including:
10. Total bilirubin
11. Alkaline phosphatase
12. Aspartate aminotransferase (AST)
13. Alanine aminotransferase (ALT)
14. Lactate dehydrogenase (LDH)
15. Albumin
16. Total Protein
17. Urinalysis

## **5.2 Exclusion Criteria**

An individual who meets any of the following criteria will be excluded from participation in this study:

1. Patient receiving less than 1200 cGy of TBI
2. Previous history of thoracic radiation therapy including previous TBI
3. All premenopausal women who have undergone menarche will require a urine qualitative pregnancy test to exclude pregnancy. Pregnant women will be excluded from the study.
4. Prisoners
5. Patient not meeting transplant criteria per BMT physician.

## **5.3 Vulnerable Subjects**

Anyone eligible for full-dose TBI based conditioning regimens as preparation for ASCT will be included in the study population and not meeting the exclusion criteria. This may include vulnerable subjects including elderly patients as well as minors ages 10-17.

Beginning in October 2020, NYU Langone Health began performing ASCT in the pediatric population. Since October 2020, 8 allogeneic transplants have been performed in the pediatric unit. NYU does not have a pediatric TBI program and thus 2 patients (both 13 years of age) who needed TBI as part of their conditioning for ASCT were referred to other institutions for their transplant. NYU's program received FACT accreditation effective 1/19/22. With the increasing volume of ASCT in our pediatric population and the FACT accreditation, it is crucial that NYU develop its TBI program to accommodate these patients. As such, we are amending this protocol to include patients ages 10 and up.

## **5.4 Strategies for Recruitment and Retention**

The inclusion and exclusion criteria in this study should not have a negative effect on the enrollment of the desired populations. Prospective subjects will receive detailed information regarding this study; its investigational nature, required study procedures, alternative treatments, risks and potential benefits of the study. They will also receive the informed consent document to read. All questions are answered by the PI and qualified research personnel.

The Principal Investigator or investigators will:

1. Obtain signed and dated informed consent from the potential subject before any study specific procedures are performed.
2. Determine patient or prospective subject eligibility (inclusion and exclusion criteria).

CONFIDENTIAL

This material is the property of the NYU School of Medicine and Langone Medical Center. Do not disclose or use except as authorized in writing by the study sponsor

3. Submit registration to NYU Langone Health Perlmutter Cancer Center CTO.
4. Receive registration confirmation from NYU Langone Health Perlmutter Cancer Center CTO, including a unique study identification number assigned to the subject that will be distributed to the study team upon registration of the subject. Confirmation of subject registration must be obtained before any treatment is administered or study procedures are performed.

Recruitment and consenting will take place in a private area such as an exam room to protect the patient's privacy. The informed consent process and documentation follows that established procedures of NYULH Human Subject Research Standard Operating Procedures (HSR 301 Informed Consent Process and Documentation).

#### **5.4.1 Use of DataCore/Epic Information for Recruitment Purposes**

This study will not utilize EPIC to identify subjects.

Any recruitment information sent by email will utilize Send Safe email.

If a subject requests information regarding opting out of further recruitment for all research, subjects will be directed to contact [[contact]](mailto:[contact]) or [name].

### **5.5 Study Duration**

The study will continue until 1 year after the day of transplant for last subject enrolled. The primary endpoint is up to 100 days post-transplant and the secondary endpoint is up to 1 year post-transplant. Accrual estimated over 15 months.

### **5.6 Total Number of Participants**

35 participants will be accrued for this study. Consenting, screening, and treatment visits will take place at NYU Langone Health PCC.

Recruitment will end when 35 participants are accrued. It is expected that fewer than 10% of patients or prospective subjects will not be evaluable for dosimetric evaluation. Up to 70 participants may sign consent in order to achieve 35 accrued subjects; this is to account for screen failures.

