### **10.1 Statistical and Analytical Plans (SAP)**

Characteristics of patients at start of TBI will be summarized using descriptive statistics. Radiation dosimetry parameters will be summarized with descriptive statistics. The proportion of patients who meet the criteria for excellent coverage based on the definition above will be estimated along with exact 95% confidence intervals.

The cumulative incidence of non-infectious idiopathic pneumonia syndrome (IPS) within the first 100 days post transplant. Additionally, the time to the first occurrence of acute GVHD, transplant related mortality or death in the first 100 days will be estimated.

Event Free Survival (EFS): interval from date of transplant to date of first objective disease progression or relapse or death from any cause. Patients without these failures will be censored at the last date that they were assessed and evaluated as failure free.

95% confidence intervals and time to event curves will be provided.

*Sample size considerations.* We consider the proportion of patients who achieve the specified dosimetric criteria. If the true rate of success with respect to the defined dosimetric criteria is 85% or greater, with 35 patients, the lower edge of the exact Clopper Pearson one sided 95% confidence interval would be  $\geq 68.9\%$ .

All treated subjects who receive a bone marrow transplant will be included in all analyses.

Distributions of patient disease and treatment regimens as well as other characteristics of patients who complete TBI and receive BMT will be compared with those of patients who do not complete TBI. Analyses of secondary and exploratory endpoints will be primarily descriptive.

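### The primary success rate has no single denominator: subjects who start TBI but stop, are not transplanted or lack dosimetry may drop out of it

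*Combined protocol and SAP*

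**What the plan says.** Four places bear on who is counted in the primary proportion.

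- **Protocol Summary, Statistical Analysis row.** The proportion is to be estimated, with an exact 95% interval, among patients who receive TBI. Transplant is not a condition.
- **Section 5.6.** "Recruitment will end when 35 participants are accrued." The next sentence reads: "It is expected that fewer than 10% of patients or prospective subjects will not be evaluable for dosimetric evaluation." The only allowance for losses is at consent: "Up to 70 participants may sign consent in order to achieve 35 accrued subjects; this is to account for screen failures." The section does not define accrued or evaluable, and gives no rule for replacing an accrued subject.
- **Section 5.4.** "Confirmation of subject registration must be obtained before any treatment is administered or study procedures are performed." Registration therefore comes before irradiation, but the section does not equate registration with accrual.
- **Section 10.1.** The analysis set is: "All treated subjects who receive a bone marrow transplant will be included in all analyses." The same section plans to compare patients who complete TBI and are transplanted with those who do not complete TBI. Its precision statement begins "If the true rate of success with respect to the defined dosimetric criteria is 85% or greater, with 35 patients" and gives a lower limit of 68.9%.

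The primary endpoint (section 4.2.1) is purely dosimetric: V100%, D98 and mean lung dose must all meet their limits.

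**The concern.** Whether a subject meets the three dosimetric limits does not depend on whether the transplant takes place afterwards. Making transplant a condition for entering the primary proportion therefore removes subjects for a reason that arises after the endpoint, and one that may be related to how the irradiation went. Section 5.6 adds a second possible exit by anticipating subjects with no usable dosimetry, while section 10.1 does not say how to score one.

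Two analysts could each follow a section of the protocol faithfully and report different primary results. In a single-arm study whose primary result is one proportion from 35 subjects, each subject removed or kept moves the estimate visibly. The choice would also be made when the outcomes are already known.

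**Working it through.** **1. Which subjects each section counts**

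| Subject | Protocol Summary | Section 5.6 | Section 10.1 |
|---|---|---|---|
| Registered, never irradiated | Out | May use one of 35 places (accrued is undefined) | Out |
| Starts TBI, does not complete it | In, if starting counts as receiving | In the accrual count | Set apart in a comparison group |
| Completes TBI, not transplanted | In | In the accrual count | Out |
| Transplanted, no usable dosimetry | In, scoring not stated | Expected, handling not stated | In, scoring not stated |
| Moved to a backup technique, transplanted | In | Not addressed | In |

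The disagreement lies in rows 2 to 4.

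**2. The plan's own figure**

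The Clopper-Pearson lower limit is L = BetaInv(α; x, n − x + 1), with α = 0.05 one-sided and 0.025 two-sided. With n = 35 and a rate of 85%, x = 0.85 × 35 = 29.75.

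- One-sided, x rounded down to 29: L = 68.94%.
- Two-sided, x = 29.75: L = 68.88%.

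Both round to the stated 68.9%. Section 10.1 labels the limit one-sided, but its analysis sentence ("will be estimated along with exact 95% confidence intervals") does not give the sidedness. Either way the calculation uses all 35, with no allowance for subjects lost from the denominator.

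**3. Cost of a smaller n alone**

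Section 5.6 gives fewer than 10%. Applied to 35 (an assumption, since its stated base also includes prospective subjects), this is fewer than 3.5, so at most 3, leaving 35 − 3 = 32. If the loss is unrelated to outcome and the rate is 85%:

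- One-sided: 71.4% at n = 35, 70.7% at n = 32 (0.8 points lower before rounding).
- Two-sided: 68.9% at n = 35, 68.0% at n = 32 (0.9 points lower).

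In whole subjects, 27/32 has a one-sided lower limit of 69.9%, still above the stated 68.9%.

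**4. Cost of a selective loss (assumed)**

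Take 29 successes among 35, the count that reproduces the plan's one-sided figure, and suppose that every dropped subject was a failure.

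| Dropped | Proportion | Shift (points) | One-sided 95% lower limit |
|---|---|---|---|
| 0 | 29/35 = 82.9% | – | 68.9% |
| 1 | 29/34 = 85.3% | +2.4 | 71.5% |
| 2 | 29/33 = 87.9% | +5.0 | 74.4% |
| 3 | 29/32 = 90.6% | +7.8 | 77.5% |

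The two-sided 95% intervals are 66.4% to 93.4% for 29/35 and 75.0% to 98.0% for 29/32.

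If all three dropped subjects were successes, the result would be (29 − 3)/32 = 26/32 = 81.3%, a shift of −1.6 points. With three dropped, the possible shift from 29/35 therefore runs from −1.6 to +7.8 points, depending on outcomes that the documents do not describe. The count of three is borrowed from section 5.6. The plan gives no figure for subjects who start TBI and are not transplanted.

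**The case against.** The strongest reply is that section 10.1 contains the only analysis-set rule, and that section 5.6 merely states an expectation about evaluability. On that view the two do not conflict. The rule also retains subjects who might be expected to fail. Section 6.1.2 allows another technique if the assigned linac is down, and section 2.1 reports V100% of 25% to 65% for the institution's conventional technique against the 90% required. A subject treated that way and then transplanted stays in under section 10.1, probably as a failure. The endpoint may also be read from the treatment plan, since section 4.2.2 describes its companion parameters as plan parameters. A stopped course would then still have values, and missing dosimetry should be rare. Finally, this is an estimation study: 85% is a planning rate, not a threshold for a decision.

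Much of this stands, and it rules out three stronger readings that a reader might infer.

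- **That recruitment closes at 35 registrations, so the analysis must fall short of 35.** Accrued is undefined. If it means treated, a never-irradiated subject takes no place. The analysis may have fewer than 35, but the text does not establish that it will.
- **That section 5.6 discards the subjects most likely to have failed.** It contains no exclusion rule and gives no reason for non-evaluability.
- **That the precision statement is materially wrong.** At n = 32 the loss is under 1 point.

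The reply does not remove the transplant condition, the difference from the Protocol Summary, or the silence on scoring. If the endpoint is a plan quantity, there is even less reason to drop a subject because transplant did not follow.

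**Conclusion.** The point holds as an inconsistency in the primary denominator. The Protocol Summary counts those who receive TBI, section 10.1 counts those who are treated and transplanted, and section 5.6 expects some subjects without dosimetry whom no section says how to score. Subjects who start TBI and then stop or do not reach transplant could leave a proportion to which their irradiation belongs.

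This could raise the reported success rate, but neither the direction nor the size can be taken from the documents. The rise of 2.4 to 7.8 points assumes 29 successes in 35 and that all of the one to three dropped subjects were failures. The effect of sample size alone is under 1 point and would not justify a change by itself. The case for acting is that the rule is cheap to settle now and depends on the result if it is settled later.

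**What to change.** **Section 10.1.** Define the primary proportion over every subject who starts study TBI, whether or not a transplant follows, including anyone switched to a backup technique. Count missing or incomplete dosimetry as not achieved. The transplant condition can stay for the endpoints measured from transplant.

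**Section 5.6.** Remove the non-evaluable allowance for treated subjects. Count accrual from the first TBI fraction, so that subjects registered but never irradiated are replaced within the existing 70 consents.

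**Cost.** A few sentences in two sections, and a few more registrations. If the 10% in section 5.6 is used as a yardstick, 35/0.90 = 38.9, so 39 registrations at most, or 4 more. Counting missing dosimetry as not achieved is a conservative convention and may lower the reported success rate slightly. Restating the precision for 32 subjects instead would gain almost nothing and would leave the denominator unsettled.

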### **5.7 Participant Withdrawal or Termination**

#### **5.7.1 Reasons for Withdrawal or Termination**

Participants are free to withdraw from participation in the study at any time upon request. An investigator may terminate participation in the study if:

- Any clinical adverse event (AE), laboratory abnormality, or other medical condition or situation occurs such that continued participation in the study would not be in the best interest of the participant
- The participant meets an exclusion criterion (either newly developed or not previously recognized) that precludes further study participation

#### **5.7.2 Handling of Participant Withdrawals or Termination**

#### **CONFIDENTIAL**

This material is the property of the NYU School of Medicine and Langone Medical Center. Do not disclose or use except as authorized in writing by the study sponsor

Withdrawal from the study can be made in writing to the Principal Investigator, [name].

## **5.8 Premature Termination or Suspension of Study**

This study may be temporarily suspended or prematurely terminated if there is sufficient reasonable cause. Written notification, documenting the reason for study suspension or termination, will be provided by the suspending or terminating party to [name] and any regulatory authorities. If the study is prematurely terminated or suspended, the PI will promptly inform the IRB and will provide the reason(s) for the termination or suspension.

Circumstances that may warrant termination or suspension include, but are not limited to:

- Determination of unexpected, significant, or unacceptable risk to participants
- Demonstration of efficacy that would warrant stopping
- Insufficient compliance to protocol requirements
- Data that are not sufficiently complete and/or evaluable
- Determination of futility

Study may resume once concerns about safety, protocol compliance, data quality are addressed and satisfy the sponsor, IRB and/or FDA.

## **6 Study Agent (Study drug, device, biologic, vaccine etc.) and/or Procedural Intervention**

### **6.1 Study Agent(s) and Control Description**

The study intervention is a VMAT based delivery technique using a 6 MV photon beam from a Varian TrueBeam® (Palo Alto, CA) equipped with a Millennium multi-leaf collimation (MLC) system^3. In a VMAT treatment, the linear accelerator gantry rotates continuously around the patient with the MLC leaves and dose rate varying throughout the arc delivery to modulate the dose to the target while selectively blocking the OARs.

The study will employ a feet first treatment plan for the lower body and a head first plan for the upper body.. Plans will be adequately overlapped and modulated to provide satisfactory coverage at the junction of the plans.

#### **6.1.1 Dosing and Administration**

Radiation dose will be administered according to the physician's written directive. Treatment will be administered twice a day over four consecutive days with an interfraction daily break of at least 6 hours between the end of the first fraction and the start of the next fraction.

Treatment will be administered by registered radiation therapists (RTTs). Prior to administration, the imaging system will be deployed to acquire kV, MV orthogonal projection radiography image(s) as well as CBCT image(s) to confirm accurate patient positioning. Optimal patient positioning shifts will be calculated and applied as deemed necessary based on acquired imaging. The imaging will be performed prior to the actual first day of treatment for the first patient (films only day). After that subject, we will re-evaluate the need for subsequent films only days. During delivery, the electronic portal imager device will be deployed to record the dose delivered to the participant. This technique, known as transit dosimetry, will be used to evaluate the accuracy of the treatment delivery as mentioned above.

### 6.1.2 Dose Adjustments/Modifications/Delays

Subjects will be treated to full dose (>12Gy) as outlined above. Adjustments to the prescription may occur at the discretion of the treating physician due to comorbidities or the participant's general condition. Dose objectives are described in section 4.2.2. Adjustments to these dose objectives may be in place at the discretion of the treating physician due to special circumstances, such as pre-irradiation and/or comorbidities outside of the thoracic region. Any modification to the outlined protocol will be noted, recorded, and taken into consideration for disease outcomes.

In the scenario that the linear accelerator used for the treatment (True Beam 1) goes down and cannot be used, and the subject needs TBI before the machine is fixed, the subject will be treated on a different machine, with whatever plan is able to be delivered (VMAT, VMAT with AP/PA, or laterals). This would likely entail adjustment of the dose objectives for the entire course. Any modification to the outlined protocol will be noted, recorded, and taken into consideration for disease outcomes.

### 6.1.3 Duration of Radiation Therapy

Radiation Treatment will be administered twice a day over four consecutive days with an interfraction daily break of at least 6 hours between the end of the first fraction and the start of the next fraction.

### 6.1.4 Tracking of Radiation Dose

Dose tracking will be performed using two different methods:

1. Reference points will be placed in the plan using Varian Eclipse treatment planning system (TPS) that tracks the prescribed dose per fraction as well as the dose at individual locations.
2. In-vivo transit dosimetry during treatment will be recorded using the electronic portal imager device (EPID). This cumulative dose images will be analyzed for each fraction to track dose delivered.

